## 3.2.10.1 Botulinum Toxin History

The following listings will be presented:

- All subjects previously treated with BTX, by subject ID
- All previous BTX treatments, by subject ID, start date, treatment and reason, including all information recorded on the eCRF for each treatment (dose, average frequency of injection and duration)
- All side effects experienced during previous BTX treatment intake, by subject ID.

The number and percentage of subjects who received any previous BTX treatment at least once will be presented by treatment group of Treatment Cycle 1. This table will summarise also the number and percentage of subjects with any significant side effects experienced. Additionally, the indication for treatment will be summarised by treatment group and overall for the mITT population.

# 3.2.10.2 Other Prior and Concomitant Therapies (Medications and Non-drug Therapies)

Prior and concomitant medications will be coded according to WHO-DD. The therapeutic class will correspond to the second level of the Anatomical Therapeutic Chemical (ATC) code, i.e. corresponding to the first 3 figures.

Prior and concomitant non-drug therapies will be coded using MedDRA.

The date of Day 1 will be used as the cut off date for the definition of a prior and concomitant therapy, so a therapy that finished before Day 1 will be considered as prior and a therapy that started on or after Day 1 will be considered as concomitant. A therapy that started before Day 1 and is continuing will be considered as prior therapy.

Listings will be presented for each of the following:

- Prior and concomitant medications other than for spasticity
- Prior and concomitant non-drug therapies
- Prior and concomitant medications for spasticity.

The medications listings will be sorted by subject ID, start date, therapeutic class, preferred name and verbatim name, whilst the non-drug therapies listing will be sorted by subject ID, start date, SOC, preferred name and verbatim name. Therapies will be flagged as prior or concomitant in the listings. Separate listings will be provided for medications for spasticity and potentially prohibited concomitant medications.

For prior records the treatment group will be assigned based on Treatment Cycle 1.

For each of the above, the number and percentage of subjects will be provided by treatment group, with separate tables for prior and concomitant records, sorted by therapeutic class and preferred name for medications, and by SOC and PT for non-

drug therapies. Prior records will be counted under the dose of Treatment Cycle 1; for concomitant records the treatment group will be the most recent Dysport dose received on or before the medication or non-drug therapy start date for the Treatment Cycle.

Prior and concomitant surgical procedures will be coded using MedDRA. Listings will present all data collected sorted by subject ID, SOC, PT, verbatim text and date of surgery, for prior surgeries and concomitant surgeries separately.

Frequency tables of the number and percentage of subjects will be provided for prior and concomitant surgical procedures separately, by SOC and PT for each treatment group and overall for the mITT population.

The prior and concomitant use of orthoses and/or splints, physiotherapy and occupational therapy, and also home excercises will be summarised in frequency tables of the number and percentage of subjects for each treatment group and overall for the mITT population. Listings will also be produced, by subject ID, start date, affected limb (if applicable), and therapy.

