7.2.1 Screening (Day -7 to Day 1, Visit 1)

Written informed consent must be signed by the parent(s)/guardian(s) of all subjects, and assent obtained from the child, when and where applicable, prior to entry into this study.

This visit may occur on the same day as the baseline visit (Visit 2 (see Section 7.2.2)) at the discretion of the Investigator. Subjects have to undergo the following assessments in order to be randomised into the study:

- Eligibility checks (inclusion/exclusion criteria).
- Demographics (date of birth/age, sex, ethnicity and race)².
- Medical/surgical history, including ongoing medical history.
- Cerebral palsy history and status.
- Botulinum toxin treatment history.
- Prior and concomitant medications. Prior medications will be all medications administered within 30 days before the screening visit and stopped either before or at study entry.
- Prior and concomitant nondrug therapies. Prior nondrug therapies will be all nondrug therapies administered within 30 days before the screening visit and stopped either before or at study entry.
- Physiotherapy and occupational therapy (frequency and intensity). Prior physiotherapy and occupational therapy will be all therapy within 90 days before the screening visit and stopped either before or at study entry.
- Use of splints and/or orthoses.
- Gross Motor Function Classification System level [44].
- Physical and neurological examinations.
- Vital signs (BP and HR) and body weight.
- A 12-lead ECG.
- Collection of AEs.

² Demographics data will be collected according to individual country requirements.

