Laboratory test results will be recorded by the central laboratory and provided to the study Sponsor, and to the study sites for evaluation of clinically significant changes. All clinically relevant abnormal laboratory tests occurring during the study will be repeated at appropriate intervals until they return to baseline or to a level deemed acceptable by the Investigator and the Sponsor's medical monitor (or his/her designated representative), or until the abnormality is explained by an appropriate diagnosis. See Section 10.1.5 for abnormal laboratory tests that should be recorded as AEs in the eCRF.

8.2.6 *Prior and Concomitant Medications*

Prior and concomitant medications will be included as a safety evaluation in this study and will be monitored from the time that the child's parent(s)/guardian(s) give informed consent to the end of the study (as defined in Section 4.3.2).

8.2.7 *Body Weight and Height*

Body weight will be measured at screening, at Day 1 of each treatment, at Week 16 of each treatment and at the end of study visit or early withdrawal.

Height will be measured at Day 1 of Treatment 1, at Week 16 of each treatment and at the end of study visit or early withdrawal.

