9.6 Concomitant Medication/Therapy

The following concomitant medications/therapies are not permitted during this study (see also Section 6.3):

- Botulinum toxin for administration into any site of the body other than Dysport in the study limb (or in the non-study upper limb and/or in the lower limbs for Treatments 2, 3 and 4).
- Any investigational new drug or device or off label use of any drug.
- Treatment with any drug that interferes either directly or indirectly with neuromuscular function (e.g. aminoglycoside antibiotics) or neuroblocking agents used during surgery (e.g. curare) within ± 30 days of any study treatment.
- Intrathecal baclofen therapy.
- Phenol or alcohol injection affecting the study limb.

The following concomitant medications are permitted during this study but they must be monitored closely and every effort should be made to keep concomitant spasticity treatment

constant throughout the course of the study. However, changes in pain medication are acceptable if absolutely necessary and according to clinical judgement (see also Section 6.3):

- Concomitant use of anticholinergic drugs (which may potentiate systemic anticholinergic effects) is permitted if the dosage has been stable for the 4 weeks prior to study treatment and is expected to remain at this stable dose throughout the study.
- Concomitant treatment with dantrolene, tizanidine, gabaergic drugs, opioid, oral baclofen or other antispasticity agents like benzodiazepines should be kept at the same dose throughout the study.

The following conditions apply for physiotherapy, occupational therapy or use of splints and/or orthoses:

- If undergoing pre-study therapy, such physiotherapy, occupational therapy or use of splints and/or orthoses, therapy must have been initiated at least 30 days prior to the baseline visit and agreed to continue the therapy throughout the study and at the minimum, up to Week 16 following the first treatment administration.
- No physiotherapy, occupational therapy or use of splints and/or orthoses should be initiated less than 30 days prior to the baseline visit or during the course of the study up to Week 16 following the first treatment administration.
- Initiation of physiotherapy, occupational therapy or use of splints and/or orthoses after Week 16 following the first treatment administration will be allowed.
- Physiotherapy and occupational therapy sessions, or use of splints and/or orthoses will be documented in the subject diary and eCRF.

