Summary statistics on the duration of QT/QTc interval and HR will be presented overall and by treatment group for each scheduled assessment visit and for both actual values and changes from baseline. Baseline values for each treatment group will be defined as the measurements collected at screening.

The number and percentage of subjects with duration of QT/QTc interval within the following three ranges of interest will also be presented overall and by treatment group for each scheduled assessment visit:

- >450 to 480 msec.
- >480 to 500 msec.
- >500 msec.

The number and percentage of subjects with an increase from baseline in the QT/QTc interval of >30 msec and >60 msec will also be presented overall and by treatment group for each scheduled post baseline assessment visit.

The number and percentage of subjects with any of the following ECG abnormalities will be provided overall and by treatment group for each scheduled assessment visit:

- Arrhythmias.
- Second degree AV block
- Third degree AV block.
- ST segment abnormalities.
- T-wave abnormalities.
- U-wave abnormalities.
- Myocardial infarction.
- Right bundle branch block
- Left bundle branch block.

Prior and Concomitant Medications

Prior and concomitant medications will be coded according to the World Health Organisation Drug Dictionary (version in force at the time of database freeze).

The date of Day 1 will be used as the cut off date for the definition of a prior and a concomitant medication. A medication that started before the cut off date and is continuing will be considered as both prior and concomitant medications.

The number and percentages of subjects will be provided overall and by treatment group for prior and concomitant medications sorted by drug class and preferred drug name.

A listing will present by treatment group the prior and concomitant medications sorted by drug class and preferred drug name. Prior and concomitant medications will be flagged in the listing.

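### SAP 3.2.10.2 treats a medication ongoing at Day 1 as prior, where Protocol 11.4.4 counts it as both prior and concomitant, so the concomitant medication tables omit stable background drugs

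*SAP*

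**What the plan says.** SAP 3.2.10.2 takes Day 1 as the cut-off for medications and non-drug therapies alike. It states that "a therapy that started on or after Day 1 will be considered as concomitant", and then: "A therapy that started before Day 1 and is continuing will be considered as prior therapy". Counts by treatment group follow, "with separate tables for prior and concomitant records". Prior records go under the Treatment Cycle 1 dose. A concomitant record goes under the latest Dysport dose given by the date the therapy began.

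Protocol 11.4.4 uses the same cut-off but speaks of medications only: "A medication that started before the cut off date and is continuing will be considered as both prior and concomitant medications".

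Three other parts of the protocol bear on this.

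- Protocol 8.2.6 gives the data their purpose: "Prior and concomitant medications will be included as a safety evaluation in this study".
- Protocol 9.6 names background drugs that may continue: "Concomitant use of anticholinergic drugs (which may potentiate systemic anticholinergic effects) is permitted if the dosage has been stable for the 4 weeks", and "Concomitant treatment with dantrolene, tizanidine, gabaergic drugs, opioid, oral baclofen or other antispasticity agents like benzodiazepines should be kept at the same dose".
- Protocol 7.2.1 uses a narrower sense of prior at screening: "Prior nondrug therapies will be all nondrug therapies administered within 30 days before the screening visit and stopped either before or at study entry". A parallel sentence there applies the same limit to medications.

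SAP Section 5 lists departures from the protocol. No visible entry mentions this one; one entry is redacted.

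**The concern.** A concomitant medication table is read as a summary of what subjects were taking while they were exposed to study treatment. Under the SAP rule it would show only what was started from Day 1 onwards. Long-standing drugs that the protocol expects to run alongside Dysport at a constant dose would be missing. They include anticholinergics, which Protocol 9.6 flags for a possible additive systemic effect.

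The prior table does not make up for this. It would hold these continuing drugs together with drugs stopped before the first injection, so neither table alone would show background use during treatment. What is at stake is the accuracy of a descriptive summary that the protocol places among its safety evaluations.

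**Working it through.** There is no planned figure to reproduce. The check is to apply each rule to the same record: a medication with complete dates, started before Day 1 and still being taken.

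| Rule | Counted as prior? | Counted as concomitant? |
|---|---|---|
| Protocol 11.4.4 | yes | yes |
| SAP 3.2.10.2 | yes | no |
| Protocol 7.2.1 (screening usage) | no, since it has not stopped | not defined there |

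The record therefore enters 2 of 2 table types under Protocol 11.4.4 and 1 of 2 under the SAP. The SAP result matches neither protocol usage, because neither makes an ongoing drug prior and nothing else.

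**Could the SAP sentence mean prior and also concomitant?** Three features of SAP 3.2.10.2 speak against it.

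1. The preceding sentence ties concomitant to a start on or after Day 1, which this record fails.
2. Tables are separate for the two classes, and listings flag each therapy as one or the other.
3. The dose group of a concomitant record is the last Dysport dose given by the therapy's start date. No study dose precedes a start before Day 1, so the rule cannot place the record in any group.

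**Worked case: an anticholinergic in use at Treatment 1.** Protocol 9.6 permits it only if the dosage was stable for 4 weeks before study treatment.

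- Required stability: 4 × 7 = 28 days.
- Latest compliant start: Day 1 minus 28 days, which is before Day 1.
- SAP class: prior.
- Compliant users counted in the SAP concomitant table for that drug: 0.

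The same follows for any antispasticity drug already being taken at baseline and held at the same dose, as Protocol 9.6 asks.

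**Which dose group would the record need?** A Group C subject is planned to receive 2 U/kg at Treatment 1 and 8 or 16 U/kg afterwards (SAP 1.2.1, Table 1). A drug taken throughout overlaps with both dose levels. Counting it under the Treatment Cycle 1 dose alone would show it only under 2 U/kg, so a correction has to cover the later cycles as well.

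**The case against.** The strongest reply concerns weight. Ongoing drugs remain in the listings and are counted by dose group in the prior tables. Medications for spasticity have their own listing and their own counts. Possible remote-spread and hypersensitivity events are assessed case by case, with concomitant medication considered for each (Protocol 10.1.4, SAP 3.2.3.1), and nothing in those sections relies on the concomitant summary table. All of this stands. A reader might infer that background drug use goes unreported or that a safety conclusion would change; the documents support neither inference.

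A second reply is that the protocol is not uniform. Protocol 7.2.1 limits prior to medications already stopped, while 11.4.4 lets a continuing one be both. This stands too, and the fix should acknowledge it. It does not rescue the SAP rule, which agrees with neither.

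Third, a reader might extend the point to physiotherapy, occupational therapy, splints and home exercises. The documents do not carry that. Protocol 11.4.4 names medications only. The closing part of SAP 3.2.10.2 summarises those therapies in frequency tables without specifying separate prior and concomitant ones, and the physiotherapy subgroup in SAP 3.2.2.7 has its own definition. For other non-drug therapy, the only protocol text in tension with the SAP is 7.2.1.

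Finally, the change cannot be called undeclared without qualification, because one entry in SAP Section 5 is redacted. The statement is limited to the visible entries.

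**Conclusion.** The two documents give different classes to the same medication record, and following the SAP as written produces concomitant medication counts that omit drugs ongoing at Day 1. The size per record is one table type instead of two. The size in subjects is unknown, since the documents do not say how many have a medication ongoing at Day 1.

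Severity is minor: the effect is confined to descriptive tables, and no efficacy result, alpha, power or safety test is touched. The conclusion rests on reading the SAP sentence with its neighbours, as set out above, and on complete dates. SAP 3.2.4.2 treats a medication with partial start and stop dates as concomitant unless those dates indicate otherwise, so some ongoing drugs with incomplete dates could still reach the concomitant table.

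**What to change.** Amend SAP 3.2.10.2 as follows.

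- A medication ongoing on Day 1 counts as both prior and concomitant, as in Protocol 11.4.4. Note beside it that Protocol 7.2.1 uses prior for medications stopped before or at study entry.
- As a concomitant record, it is counted under the Treatment Cycle 1 dose and under the dose of each later Treatment Cycle during which it is still being taken.
- For non-drug therapy, where Protocol 11.4.4 is silent, say whether the same rule applies, in a way consistent with Protocol 7.2.1.

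If prior-only is intended, keep the rule and declare it with a reason in SAP Section 5.

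The cost is a few sentences of SAP text, a class flag, and a per-cycle check of whether the medication is still in use. Data collection and the efficacy analyses do not change.

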## 3.2.11 Pharmacokinetics and Antibodies

All results from testing for presence of BTX-A-Abs (binding and neutralising) will be listed, sorted by subject ID and assessment visit. Two additional listings will be provided, one for all subjects with positive binding antibodies post baseline, one for all subjects with positive neutralizing antibodies post baseline. These listings will include the combined information about baseline BTX status, MAS and PGA results, and TEAEs for each subject.

Summary tables for positive/negative BTX-A-Abs with the number and percentage of subjects at baseline and at EOS/EW will be provided for both neutralising and binding antibodies. Additionally a shift table from baseline to the EOS/EW visit will be presented with the number and percentage of subjects separately for binding and neutralising antibodies. EOS/EW records will be counted under the dose of the last Treatment received.

3.2.12 Pharmacodynamics

Not applicable.

## 3.2.13 Derived Data

3.2.13.1 Age

Subject age (months) will be derived as (screening visit date birth date)/30.4375.

3.2.13.2 Body Mass Index

Body mass index  $(kg/m^2)$  will be derived as Weight  $(kg)/(\text{Height}(cm)/100)^2$  and rounded to the nearest decimal.

Body mass index classes are defined in section 8.2.

3.2.13.3 Therapeutic Class

The therapeutic class for medications corresponds to level 2 of the ATC code and will be derived as the first 3 characters of the ATC code.

The decoding of the therapeutic class will be done from the WHO-Drug Dictionary version in effect within the sponsor company at the time of database lock.

## 3.2.13.4 Changes from Baseline

Changes from baseline to any visit will be calculated as a difference from baseline (e.g. assessment at the visit assessment at baseline).

3.2.13.5 Adverse Event Duration

If the start and end dates of the AE are identical then "<1" day will be presented with the duration in hh:mm recorded in the eCRF if it is available. If times are available, the duration will be calculated as (end date/time start date/time) and presented in days hh:mm. If at least one time is missing and if the duration is greater than 24 hours then it will be calculated as (end date - start date)+1 and presented in days. If the recorded end date is CONT. (for continuing), the end date will be listed as "ongoing" and the duration will be approximated as " $\geq$ (last attended visit date start date)+1" day(s). If the start date or the end date are partial the duration will be presented as a superior inequality " $\geq$ xx" day(s) (i.e.:  $\geq$ 2 where start date=31JAN2004 and end date=FEB2004 or start date=JAN2004 and end date=01FEB2004]).

## 3.2.13.6 Adverse Event Episode Duration

If there are several episodes of the same AE then the end date of any episode prior to the last one will be imputed as (start date of the next episode 1 day) and the duration of the AE episode will be calculated using this imputed end date by the following formula (end date of the episode - start date of the episode) + 1.

3.2.13.7 Time since Study Treatment Administration for Adverse Event

If the start date of the AE is identical to the date of the study treatment administration, then"<1 day" will be presented with the time to onset in hh:mm recorded in the eCRF if it is available.

If times are available, the time will be calculated as (start date/time last administration date/time) and presented in days hh:mm.

If at least one time is missing and if the time to onset is greater than 24 hours then it will be calculated as (start date - last administration date) + 1 and presented in days.

If the start date is partial, the time since study treatment administration will be presented as a superior inequality (i.e.: for an AE started in FEB2004 after the only administration performed on 31JAN2004, the time will be presented as " $\geq$ 2" days). If the start date is missing the time since study treatment administration will not be presented.

3.2.13.8 Study Duration (all Treatment Cycles)

Study duration in weeks will be calculated as ((date of last visit attended screening visit date) + 1) / 7.

# 3.2.13.9 Treatment Cycle Duration

For subjects who are retreated at the end of a Treatment Cycle, the Treatment Cycle duration will be calculated, and presented in days, as:

Treatment Cycle Duration = (Date of retreatment) (Treatment injection date).

For subjects who are not retreated at the end of a Treatment Cycle, the Treatment Cycle duration will be calculated as:

Treatment Cycle Duration = (Treatment Cycle last attended visit date) (Treatment injection date) + 1.

3.2.13.10 Study Treatment Exposure (all Treatments)

Study treatment exposure in weeks will be calculated as ((date of last visit attended Treatment Cycle 1 injection date) + 1) / 7.

## 3.2.13.11 Treatment Cycle Exposure

For any of the Treatment Cycles, the Treatment Cycle exposure in weeks is calculated as:

(Last attended visit date in the Treatment Cycle Treatment Cycle injection date + 1) / 7.

## 3.2.13.12 Time Intervals between Treatments

For each Treatment Cycle the time interval between treatments will be calculated, and presented in days, as:

(Treatment injection date of the next Treatment Cycle - Treatment injection date) + 1

